## 14 Efficacy Analyses

## 14.1 Primary Endpoint: ARR

## 14.1.1 Primary Objective: Analysis of the ARR

Analysis (Analysis	Derivation	Statistical Analysis Methods	Missing data handling
Population)			
Primary endp	oint: ARR over 24 Month	S	
Primary (FAS)	ARR over 24 Months. The ARR over 24 Months of a patient is calculated as the number of relapses of the patient divided by the number of days on study for that patient and multiplied by	The population estimate will be based on the average of the ARR values for the patients in the study. The corresponding 95% CI will be reported. The Statistical Analysis Software (SAS) ® MEANS procedure will be used to compute these quantities. The following descriptive statistics will be reported: mean,	Patients discontinuing early are analyzed according to number of years of follow-up on treatment and number of relapses observed at the time of discontinuation.
Secondary (PP)	365.25. This variable will be considered to get population estimates.	SD, min, max, median, first quartile (Q1) and third quartile (Q3).	
	A relapse will be defined as per routine clinical practice as determined by the investigator		
	Time on Study (days) = (Date of Study Completion or Date of study discontinuation - Date of first dose of cladribine tablets +1)		
Sensitivity (FAS)	Model based ARR, defined as expectation of relapses divided by time on study.	The estimate of the expected ARR at Month 24 will be based on a Negative Binomial (NB) model for relapse count, with offset equal to the log of years on study and adjustment for categorical number of relapses in the last 2 years, or since MS diagnosis if diagnosis <24 months (≤1 relapse, >1 relapse). The NB regression will be computed with the SAS ® GENMOD procedure, using the dist=NB option in the MODEL statement	Same handling as for the primary analysis

Analysis (Analysis Population)	Derivation	Statistical Analysis Methods	Missing data handling
		*The estimate of the expected ARR at Month 24 will be based on a Zero Inflated NB model for relapse count, with offset equal to the log of years on study and adjustment for categorical number of relapses in the last 2 years, or since MS diagnosis if diagnosis <24 months (≤1 relapse, >1 relapse). The NB regression will be computed with the SAS ® GENMOD procedure, using the dist=ZINB option in the MODEL statement.	

ARR: Annualized Relapsed Rate; FAS: Full Analysis Set; GENMOD: Generalized Linear Model PP: Per Protocol; SAS: Statistical Analysis System.

\* The sensitivity analysis with the zero inflated binomial model will be considered only if the number of patients without relapses is greater than 5%.

The primary endpoint is derived from the number of relapses collected through the eCRF forms "MS Relapse Report" and "MS Relapse Report Details". A patient will have 0 relapses (at Visit 3 and /or Visit 6) if replied "No" to the leading question "Has patient experienced a new MS relapse since last scheduled or unscheduled visit? (Yes, No)". For patient replying 'Yes', the number of relapses will be derived from the records in the "MS Relapse Report Details" form. If at Visit 3 the answer to the leading question is not collected, then the number of relapses in the first year and the total number of relapses during the second year will be missing. If at Visit 6 the answer to the leading question is not collected, then the number of relapses during the second year will be missing.

For ongoing patients during the study, the Time on Study will take into account the last available date of a patient. This will be used in the interim analyses for all ARR evaluations (primary objective, sensitivity analyses and secondary analyses).

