## 14.1.2Sensitivity Analyses of the ARR

For the NB model the Least Squares means estimates of the ARR at Month 24 and associated CI will be reported for patients having respectively  $\leq 1$  relapse or >1 relapse in the previous 2 years, or since MS diagnosis if diagnosis <24 months. These quantities will be obtained using the LSMEANS statement with the ILINK option.

For the Zero Inflated NB model, the following approach will be used to report the estimates of the ARR at Month 24 and associated CIs for patients having respectively  $\leq 1$  relapse or >1 relapse in the previous 2 years, or since MS diagnosis if diagnosis <24 months. The STORE statement in PROC GENMOD will be used to save the fitted model. Then the fitted model will be used in proc PLM with the SCORE statement and the ILINK and NOOFFSET option.

Standardized deviance residuals will be plotted against the linear predictor to assess the goodness of fit of the model (NB or Zero inflated NB). The STDRESDEV statement with the XBETA option in the GENMOD procedure will be used.

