## 14.1.4 Subgroup Analyses of ARR

The subgroup analyses of the primary endpoint (at Month 24 for the ARR during the follow-up period) will be conducted on the FAS population.

A subgroup analysis at Month 24 of the ARR during the follow-up period for patients completing the study and patients who drop out will be performed. Estimates and CIs for the 2 subgroups will be reported using the same method of the primary analysis.

The same analysis will be performed for patients completing the treatment and patients who do not complete the treatment (i.e., completing Year 1 treatment but not Year 2 treatment) when the number of patients in the last group is greater than 10.

A subgroup analysis at Month 24 of the ARR during the follow-up period will be performed with reference to the type of MS at screening (RRMS, aSPMS, PPMS and CIS).

For the primary outcome, the patterns of missingness will be explored. When the number of missing values is substantial (>5%), multiple imputation methodology will be considered for the analysis of the primary objective. At least 20 imputed datasets will be considered. The ARR at Month 24 for a patient will be considered missing if for that patient the number of relapses at Month 24 is missing or if the Time on Study for that patient is missing. At least the following variables will be considered in the imputation model:

- ARR at Month 24
- Type of MS at screening
- Number of relapses in the previous 2 years
- Age
- Sex
- Baseline Body Mass Index (BMI)
- Compliance

Since we have both continuous and categorical variables in the imputation model the Fully Conditional Specification method will be considered for the imputation. Predictive mean matching will be used for the imputation of the following variables: ARR at Month 24, number of relapses in the previous 2 years, age, baseline BMI and compliance. SAS code for the analysis is available in the appendices.

CCI

Cladribine CLICK-MS MS700568\_0078 Version 7.0

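### The primary ARR averages patient relapse/time ratios with equal weight and no minimum follow-up, has no overall person-time ARR beside it in the readable SAP, and has conflicting rules for early leavers

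*SAP*

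**What the plan says.** **Estimator.** In SAP 14.1.1 a patient's ARR is "calculated as the number of relapses of the patient divided by the number of days on study for that patient and multiplied by" 365.25. Then "The population estimate will be based on the average of the ARR values for the patients in the study", using PROC MEANS with a 95% CI. Time on Study runs from first dose to completion or discontinuation. The Full Analysis Set (FAS) needs one dose (SAP 8.2), and no minimum follow-up is stated.

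**Person-time models.** The negative binomial (NB) and zero-inflated NB sensitivity models carry an offset of log years on study. SAP 14.1.2 reports the NB result by stratum: "Least Squares means estimates of the ARR at Month 24 and associated CI will be reported for patients having respectively" at most one, or more than one, prior relapse. The zero-inflated model is reported in the same two strata.

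**Early leavers.**
- The missing-data column of SAP 14.1.1 says: "Patients discontinuing early are analyzed according to number of years of follow-up on treatment and number of relapses observed at the time of discontinuation". SAP 14.1.4 fits this rule, since a subgroup analysis of the "ARR during the follow-up period for patients completing the study and patients who drop out will be performed".
- The text under the table in 14.1.1 says: "If at Visit 3 the answer to the leading question is not collected, then the number of relapses in the first year" and that of the second year are both missing. It continues: "If at Visit 6 the answer to the leading question is not collected, then the number of relapses during the second year" is missing. SAP 14.1.4 adds that a patient's Month 24 ARR "will be considered missing if for that patient the number of relapses at Month 24 is missing". Multiple imputation is then only to be considered, and only above 5% missing.

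**Relapse data.** Protocol 9.1.1 limits collection of post-enrollment counts to Months 12 and 24. Footnote i of Protocol Table 1 has relapse counts recorded continuously on a running page.

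**The concern.** Estimating this ARR in a single cohort is the only primary objective. A mean of ratios gives a patient seen for two months the same weight as one seen for two years. If some relapses are soon followed by study exit, those patients supply a relapse over a short denominator and pull the mean up. A pooled rate, or an NB model with a time offset, is far less exposed.

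The two early-leaver rules then matter a great deal. A patient who leaves before Visit 3 or Visit 6 has no answer collected there, so one rule keeps that patient's relapses and the other removes them. Nothing says which prevails, or that the last visit held stands in for Visit 3 or 6. Two programmers could each follow the SAP and report different primary results. SAP 14.1.1 also mixes days on study with follow-up on treatment, although Protocol 9.2.3 continues follow-up after cladribine is stopped.

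A smaller point concerns the retrospective ARR (SAP 11.3). It is also per patient, but its denominator is 24 months, or time since diagnosis if shorter, which inclusion criterion 4 makes at least 12 months. The prospective denominator has no floor.

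**Working it through.** The supplied text gives no study size, expected ARR, dropout rate or lag from relapse to exit, so there is no plan figure to reproduce. The formulas come from SAP 14.1.1; every other input below is an assumption.

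**1. One patient, observed-data rule**

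Patient ARR = relapses / days × 365.25. For one relapse:
- exit at day 30: 365.25/30 = 12.18
- exit at day 60: 365.25/60 = 6.09
- exit at day 180: 365.25/180 = 2.03
- full 24 months (730.5 days): 0.50

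Among 100 patients, the day-60 leaver adds 6.09/100 = 0.061 to the mean. In a pooled rate over about 200 patient-years, one relapse adds 1/200 = 0.005. In the retrospective ARR, with at least 12 months in the denominator, one relapse gives at most about 1.0 per year.

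**2. One day-30 leaver added to a cohort followed for 24 months**

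- N = 100: the other 99 have 30 relapses in 198 patient-years (0.152). Mean of ratios = (30/2 + 12.175)/100 = 0.272. Pooled = 31/198.08 = 0.157.
- N = 200: the other 199 have 60 relapses in 398 patient-years (0.151). Mean of ratios = (60/2 + 12.175)/200 = 0.211. Pooled = 61/398.08 = 0.153.

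**3. Simulation, exit related to relapse**

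Assumed: n = 100, gamma-Poisson counts (gamma shape 1), true ARR 0.10 and 0.20, 24 months planned, 10% other dropout uniform over 1 to 24 months, and each relapse leading to exit with a given probability after a given lag. There were 3,000 runs per cell (Monte Carlo error 0.3 to 1.2 points). Relative bias of the primary mean:

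| Rule | Relapses leading to exit | Lag 1 month | 3 months | 6 months | 12 months |
|---|---|---|---|---|---|
| Observed data | 10% | +21 to +24% | +11% | +6% | +1 to +2% |
| Observed data | 30% | +59 to +61% | +31 to +35% | +17% | +5 to +6% |
| ARR missing, no imputation | 10% | -10 to -13% | -11 to -12% | -9 to -10% | -6 to -7% |
| ARR missing, no imputation | 30% | -32 to -36% | -29 to -34% | -27 to -29% | -17 to -20% |

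With the lag spread evenly over 1 to 12 months, the observed-data rule gives +7% (10% leading to exit) and +20 to +21% (30%). In the cells of the table the pooled rate is off by +1 to -5%, and an intercept-only NB model with log-time offset by less than 2%.

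**4. Does imputation repair the missing rule?**

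The variables listed in SAP 14.1.4 do not include relapses seen before exit. With predictive mean matching (20 imputations) on age, weight, sex and prior relapses, the error shrinks by only 0 to 2 points:
- ARR 0.20, 30%, 1 month: -36.3% becomes -34.1%.
- ARR 0.10, 10%, 3 months: -10.9% becomes -10.7%.

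Compliance and MS type were not simulated, and the SAP allows further variables.

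**5. Exit unrelated to relapse**

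Assumed n = 50 to 200 and dropout of 10% or 30%. Bias is about zero. The variance of the mean of ratios is 1.11 to 1.34 times that of the pooled rate. Coverage of the 95% CI is 89 to 94%, against 91 to 95% for a robust pooled CI and 92 to 96% for NB.

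**The case against.** The study is single-arm and descriptive, and a mean of patient ARRs is a defined, pre-specified quantity. If exit is unrelated to relapse, it is unbiased and its standard error is only about 5 to 16% larger (√1.11 = 1.05, √1.34 = 1.16). Nothing in the documents shows that relapse leads to study exit, and stopping cladribine does not end follow-up. The largest biases need 30% of relapses to cause exit within a month. An NB model with a time offset is already planned. The per-protocol set requires both yearly courses, so very short denominators cannot arise there. SAP 14.2 is blacked out and may hold more. On the rules, an answer not collected could mean a visit that was held with the question left blank, and dated relapse records could reconcile the two protocol statements on collection. No comparison of prospective with retrospective ARR is planned in the readable text.

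Much of this stands as a limit. The inflation is conditional and its size unknown, and so is the downward bias, which also needs relapse-related exit. The retrospective contrast breaks no stated analysis. It does not remove the two main gaps. No text confines the missing rule to visits that were held. The NB strata bracket an overall rate and the minimum, maximum and completer/drop-out split may hint at trouble, but none gives an overall person-time figure. An overall NB estimate would also suit Protocol 9.7.3, which names an NB model with time and does not split it by prior relapse.

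**Conclusion.** The concern holds and should be fixed, with medium confidence about how much it matters. That the readable SAP lacks an overall person-time ARR, and that its rules for early leavers conflict, follows from the text and needs no assumption.

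The size does rest on assumptions. If 10 to 30% of relapses lead to exit within 1 to 12 months, the primary mean is too high by about 1 to 61% under the observed-data rule, or too low by about 6 to 36% if every early leaver is set to missing, the strictest reading of that rule. These are alternatives and cannot both occur. The lag from relapse to exit drives the inflation most: at 12 months it is 6% or less. If exit is unrelated to relapse, the cost is modest lost precision and slightly low coverage.

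**What to change.** 1. **Add an overall companion estimate.** Keep the current primary. Pre-specify beside it one overall FAS ARR with 95% CI: either an intercept-only NB model with a log(years on study) offset, or total relapses over total patient-years with an overdispersion-robust CI. SAP 15.1 already uses total events over total time for adverse events. Report the same figure for the subgroups, the per-protocol set and the retrospective ARR, so that like is shown with like; it matters least for the per-protocol set.
2. **State one early-leaver rule.** Use relapses and Time on Study up to exit wherever relapse status to exit is known. Keep the missing category for patients whose status over their observed time is unknown, and report how many there are. Say that the denominator is Time on Study, not time on treatment.
3. **Reconcile Protocol 9.1.1 with Table 1 footnote i.** Confirm which relapse data exist for patients who leave before Visit 3 or Visit 6.

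Make changes 1 and 2 together: the observed-data rule alone leaves the primary open to inflation. The cost is SAP wording and a few lines of SAS, after the check in step 3; where no relapse data exist, those patients stay missing. The downside is a second ARR figure that may differ from the primary and from interim figures.

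### SAP 14.1.1 lets a No to a since-last-visit question at Visits 3 and 6 score zero relapses, so relapses dated before the preceding visit can drop out of the primary ARR

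*SAP*

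**What the plan says.** The rule is in SAP 14.1.1.

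- **Source of the count.** The notes under the table begin "The primary endpoint is derived from the number of relapses collected through the eCRF forms" and name two forms, MS Relapse Report and MS Relapse Report Details.
- **Zero rule.** "A patient will have 0 relapses (at Visit 3 and /or Visit 6) if replied" No to the leading question, which asks "Has patient experienced a new MS relapse since last scheduled or unscheduled visit".
- **After a Yes.** Here "the number of relapses will be derived from the records in the" Details form. No sentence says what happens to Details records after a No.
- **Uncollected answer.** "If at Visit 3 the answer to the leading question is not collected, then the number of relapses in the first year" is set to missing, together with the second-year total. An uncollected Visit 6 answer makes the second-year count missing.
- **ARR.** The derivation is "the number of relapses of the patient divided by the number of days on study for that patient", scaled to a year. The Time on Study formula ends with "Date of first dose of cladribine tablets +1", so it includes every day from first dose.
- **Early discontinuation.** These patients are analyzed on the "number of relapses observed at the time of discontinuation".

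The protocol describes collection in two ways. Section 9.1.1 expects visits at about Months 2, 6, 12, 14, 18 and 24 but restricts relapse counts to Months 12 and 24, and the relapse row of Table 1 is marked only at Visits 3 and 6. Footnote i of Table 1 instead puts relapse counts on a running page that is kept up to date throughout. Section 9.3 collects an onset date for each on-study relapse, and Section 11.1 refers to a relapse module in the eCRF.

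**The concern.** The look-back of the leading question is one inter-visit interval, but the missing-answer sentences make its answer stand for a year. If the zero rule is programmed as written, a relapse seen and dated at Month 4 can disappear when the Month 12 answer is No, because nothing new has happened since Month 6. The patient's follow-up time is unaffected. An error from this rule can therefore only lower the primary ARR.

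No planned analysis would show it. The negative binomial and zero-inflated models also work on the relapse count, and the per-protocol analysis repeats the primary method. Multiple imputation (SAP 14.1.4) applies only when the count or the time on study is missing, and a false zero is not missing. The retrospective ARR (SAP 11.3) counts relapses in a 24-month window with no such question, so a loss would affect only the on-treatment figure. No formal before-after comparison is planned, but both figures are reported and a reader would set them side by side.

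**Working it through.** The documents give no figure for this point, so there is none to reproduce. The check is how much of Time on Study the two answers cover when read literally.

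**Inputs.** Visits at Months 2, 6, 12, 14, 18 and 24 (protocol 9.1.1). Year 2 visits move by at most 6 months if treatment is delayed (SAP 6). The denominator runs from first dose (SAP 14.1.1).

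**Step 1: share of follow-up outside the look-back (w).**

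| Attendance | Months inside | Months outside | w |
|---|---|---|---|
| On schedule | (12 − 6) + (24 − 18) = 12 of 24 | 12 | 50% |
| Months 6 and 18 missed | (12 − 2) + (24 − 14) = 20 of 24 | 4 | 17% |
| Only Months 12 and 24 attended | 24 of 24 | 0 | 0% |
| One patient with full 6-month delay (visits at 20, 24, 30) | (12 − 6) + (30 − 24) = 12 of 30 | 18 | 60% |

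An unscheduled visit inside a look-back shortens it and raises w.

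**Step 2: effect on the ARR.** Let f be the share of relapses in the outside months that are actually dropped. At a constant relapse rate (assumption), relative understatement = w × f. The documents do not give f, so the whole range is shown for on-schedule visits:

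- f = 0: 0%
- f = 0.10: 0.50 × 0.10 = 5%
- f = 0.25: 0.50 × 0.25 = 12.5%
- f = 1: 50%

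**Step 3: a milder literal reading.** The notes put no date limit on Details records after a Yes. Suppose a Yes brings in all of that year's records and only a No removes them. With Poisson relapses and h = rate/2 per half-year, the expected yearly count is h + h(1 − e^(−h)). The true ARRs below are assumptions.

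| True ARR | Scored ARR | Loss |
|---|---|---|
| 0.10 | 0.05 + 0.05 × 0.0488 = 0.052 | 48% |
| 0.20 | 0.10 + 0.10 × 0.0952 = 0.110 | 45% |
| 0.40 | 0.20 + 0.20 × 0.1813 = 0.236 | 41% |

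A simulation at 0.20 gave 0.100 when records after a Yes are also cut to the look-back, and 0.109 under the milder reading.

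**Step 4: effect per relapse.** One dropped relapse over 24 months lowers that patient's ARR by 12/24 = 0.5, hence the mean of 100 such patients by 0.005. Over 30 months the figures are 12/30 = 0.4 and 0.004.

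**Step 5: after the fix.** If every dated on-study record counts, coverage is 24 of 24 months and this rule causes no loss.

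**The case against.** The eCRF is not shown, and each protocol account of collection, taken alone, covers all follow-up. If the form is completed only at Months 12 and 24, a No may have been meant for the whole year. If relapses go on a running page, the question is asked at each contact and the intervals join up. A loss needs a mixture: answers used only at Visits 3 and 6, read with a per-visit look-back, and earlier dated records ignored. The general definitions also point toward counting everything. The ARR is built on the patient's relapses, the notes open with what both forms collect, and the zero can be read as limited to that visit's report.

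Much of this stands, and it is why no loss can be asserted. It does not settle the derivation. The running page and the dated variables concern collection, and the SAP rule does not refer to them. The mention of unscheduled visits fits poorly with a yearly question. Two programmers following SAP 14.1.1 could reach different numerators.

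The objection is also right about the size. A reader might infer that the ARR is halved, or that 50% is the most that could be lost. The documents support neither. The 50% requires on-schedule visits, literal answers and records after a Yes also cut to the look-back; the milder reading gives 41 to 48%, unscheduled visits could push the loss above 50%, and the ordinary readings give zero. The 60% describes a patient with the full delay, not the study mean. The contrast with the retrospective ARR is not evidence of inconsistent handling, because that history is taken once, at baseline.

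**Conclusion.** The point holds as a defect in the derivation rule, not as a demonstrated bias. SAP 14.1.1 ties a zero to an answer whose wording covers only the last inter-visit interval, and it does not say that relapses dated before the preceding visit still count. That the Visit 3 answer governs the first year is inferred from the missing-answer sentences. Any resulting error in the primary ARR is downward.

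Its size is unknown. It is zero if the running page was used and all dated records are counted, or if the answers were defined to cover the year. Under literal answers and on-schedule visits, half of the 24 months falls outside the look-back, and the percentage losses shown rest on a constant relapse rate and an unknown f. Because this is the numerator of the primary endpoint and the correction is cheap, it should be made before lock.

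**What to change.** In SAP 14.1.1, replace the zero rule with a definition along these lines:

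> The number of relapses is the count of all MS Relapse Report Details records with onset from first dose to the end of Time on Study, whatever the visit of entry and whatever the leading answer. A No sets zero only for the interval it covers, and only where no dated record falls in that interval.

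Then:

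- State which interval the Visit 3 and Visit 6 answers cover. If sites were told that they cover the whole year, say so; the interval is then that year.
- Query a No that conflicts with a dated record in the interval it covers, and any interval that no answer or record covers. Under a running page, a No at Month 12 beside a Month 4 record is expected and needs no query.
- Reconcile protocol 9.1.1 (Months 12 and 24 only) with footnote i of Table 1 (running page) on when relapses are captured.

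The cost is SAP wording, a little programming and targeted queries. The planned last visit (30 March 2024) and planned lock (3 June 2024) are 1 + 30 + 31 + 3 = 65 days apart. No new data item is needed, because onset dates are already collected. The reported ARR may become less favorable. If all dated records are already counted, the wording closes the point and no result changes.
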